4. INTRODUCTION

The purpose of this statistical analysis plan (SAP) is to describe the framework for the reporting, summarization and statistical analysis methodology of the safety, tolerability, pharmacokinetic (PK), pharmacodynamics (PD) and efficacy endpoints measured throughout the study. It is based on Protocol TB006AD2102 Amendment 2.0 dated 15 October 2021.

5. TRIAL OBJECTIVES

5.1. PRIMARY OBJECTIVES

The study is planned to conduct in two different parts, and primary objectives for Part 1 are as listed:

- To determine the safety and tolerability of multiple doses of TB006
- To determine the PK profile of multiple doses of TB006
- To determine the maximum tolerated dose of multiple doses of TB006
- To assess the immunogenicity of TB006 (production of anti-TB006 antibody)

The primary objective for Part 2 is as follows:

- To determine the clinical efficacy of TB006 in patients with mild to severe Alzheimer's disease (AD)

5.2. SECONDARY OBJECTIVES

There is no secondary objective planned for Part 1 of the study.

The following are the secondary objectives for the Part 2 of the study:

- To determine the clinical efficacy of TB006 in patients with mild to severe AD
- To determine the safety and tolerability of multiple doses of TB006
- To determine the PK following multiple doses of TB006

6. STUDY DESIGN CONSIDERATIONS

6.1. STUDY DESIGN

This is a seamless, two-part Phase 1b/Phase 2a, multi-center, randomized, double-blind, placebo-controlled study. Part 1 is a multiple ascending dose (MAD) escalation study to evaluate the safety, tolerability, PK, PD, and efficacy of TB006 in patients with AD. Part 2 is a multi-center, randomized, double-blind, placebo-controlled, parallel-group study to evaluate the efficacy of TB006 after 1 month of treatment. The total study duration for each patient will be up to approximately 19 weeks.

Patients will receive a total of 5 doses, given in qw intervals. In Part 1, the planned starting dose in Group 1 will be 140 mg qw for 5 weeks. Subsequent planned doses are 420 and 1,000 mg qw for Groups 2 and 3, respectively. The planned dose in Part 2 will be the highest safe and well-tolerated dose from Part 1. All doses are infused IV over 1 hour. Part 1 will interleave with the single ascending dose (SAD) study (Study TB006HV1101). Each group in Part 1 will commence after the safety, tolerability, and PK of the single dose equivalent to the combined total of 5 qw doses planned in this study has been established. Explicitly, dosing in Group 1 (140 mg qw) will commence when the safety and tolerability of the 700 mg single dose in the SAD study has been established. Groups 2 (420 mg qw) and 3 (1000 mg qw) will begin after a review of the available safety, tolerability, and PK data from the previous group; and after the 2,100 and 5,000 mg single dose, respectively, has been administered. Dose levels may be adjusted depending on the safety, tolerability, and available PK of doses in the SAD study and previous groups in this study. Patients will be enrolled across all active centers into each dose group sequentially.

In Part 1, 8 patients will be enrolled into each dose group; 6 patients in each group will be randomized to active TB006 treatment, and 2 patients to placebo.

Dose escalation decisions will use safety, tolerability, and available PK data through the first dose administered to the last patient in each group and a minimum of 14 days from the respective dose group that has been dosed in the SAD study (Protocol number TB006HV1101). Data will be reviewed by a blinded Safety Review Committee (SRC).

[figure not shown]
Part 2 will commence after the last patient in Part 1 has received their first dose. The planned dose in Part 2 will be 1,000 mg qw × 5 doses, but may be adjusted depending on the safety and tolerability of the doses in Part 1. Patients will be randomized to active TB006 or placebo (1:1) and will follow the same dosing schedule and procedures (with some exceptions – see Part 2 schedule of assessment) as in Part 1. Randomization in Part 2 will be stratified according to baseline patient severity, with mild AD patients [Mini-Mental State Examination (MMSE) 21-24] and moderate-severe AD patients (MMSE ≤ 20) in each stratum.

This is an outpatient study. Patients will return to the clinic for screening and baseline procedures, on dosing days, and on follow-up visits. Patients will have the option of checking into the clinic and staying overnight on Day -2 or Day -1, as well as on days prior to the other dosing days.

Assessments for safety and tolerability, efficacy, PK, and PD are performed throughout the study. If a patient reports any adverse events (AEs), they may be required to return to the clinical

unit at the discretion of the investigator for additional assessments. All AEs must be followed to adequate resolution.

[figure not shown]
Figure 1 Study Design and Treatment Schema for Part 1 and Part 2

* Study drug administration

Note: Visit days and procedures will occur during a window of \pm 2 days from Day 1 to End of Treatment.
D = Day; IV = intravenously, qw = weekly.

Figure 2. Study Design and Treatment Schema – Interleave with Study TB006HV1101

Dosing in Group 1 (140 mg TB006/placebo aww) will commence when the safety and tolerability of the 700 mg single dose in the SAD study has been established. Groups 2 (420 mg TB006/placebo qw) and 3 (1,000 mg TB006/placebo qw) will begin after a review of the available safety, tolerability and PK data from the previous group; and after the 2,100 and 5,000 mg, respectively, have been administered.

* Study drug administration

Note: Visit days and procedures will occur during a window of \pm 2 days from Day 1 to End of Treatment

D = Day; IV = intravenously; PK = pharmacokinetic; qw = weekly; SAD = single ascending dose.

6.1.1. JUSTIFICATION OF SAMPLE SIZE

In Part 1, patients will be recruited sequentially in separate increasing dose groups, with each group randomizing 6 patients to a specific dose of TB006 and 2 randomized to placebo. If all 3 planned dose levels are investigated, the study will recruit approximately 24 patients in total (18 receiving TB006 treatment at the different dose levels, and 6 receiving placebo).

In Part 2, patients will be randomized to TB006 or placebo in a 1:1 ratio so that approximately 58 patients will be randomized to each group. Randomization in Part 2 will be stratified according to baseline patient severity, with mild AD patients (MMSE 21-24) and moderate-severe AD patients (MMSE ≤ 20) in each stratum. Patients enrolled at the same TB006 dose level in Part 1, as well as all placebo patients, will be included in the efficacy analyses in Part 2. Thus, the number of patients in each group for the primary efficacy analysis will be approximately 64.

Assuming that the standard deviation (SD) of change from baseline (CFB) Clinical Dementia Rating Scale (CDRS) - Sum of Boxes at Day 104 is 0.5, a total of 128 patients will provide 80% power to detect a mean CFB difference of 0.25 at Day 104 using a 2-sided, 2 sample t-test at the 5% level of significance.

6.2. EFFICACY ENDPOINTS

For Part 1, there is no efficacy endpoint planned for primary and secondary analysis, but following endpoints is planned for exploratory analysis:

- CFB through end of study on the CDRS – Sum of Boxes total score
- CFB through end of study on the Cognitive Drug Research (CDR) System Battery Score, composite scores, and individual task measures
- CFB through end of study on the MMSE score
- CFB through end of study on the Neuropsychiatric Inventory (NPI) score

For Part 2, the planned primary efficacy endpoint is:

- CFB through Day 104 on the CDRS – Sum of Boxes total score.

And the associated secondary endpoints are as under:

- CFB through Day 36 on the CDRS – Sum of Boxes total score
- Proportion of responders on the CDRS – Sum of Boxes at Days 36 and 104
- CFB to Days 36 and 104 on the CDR System Battery, composite scores, and individual task measures
- CFB to Days 36 and 104 on the MMSE score
- CFB to Days 36 and 104 on the NPI score

6.3. SAFETY ENDPOINTS

The safety endpoints for Part 1 and Part 2 of the study will be recorded and reported throughout the safety reporting period. The safety reporting period is from Day 1 (start of TB006 infusion) through Day 104. Safety endpoints for both protocol parts of this study include:

- Incidence of AEs and serious adverse events (SAEs)

- Clinical Safety Laboratory Assessments
- Vital Signs
- Electrocardiograms
- Suicidal Ideation and Behavior Risk Monitoring
- Physical and Neurological Examinations

The safety endpoints listed above will be reported as primary endpoints for Part 1 of the study and as secondary endpoints for Part 2 of the study.

6.4. PHARMACOKINETIC ENDPOINTS

The PK analysis will be performed using PK parameters derived by non-compartmental analysis (NCA) using the TB006 plasma concentration time data. The PK parameters will be estimated using actual sampling time relative to the start of infusion.

For Part 1 of the study, the PK analysis will be performed as primary endpoint and includes, but not limited to:

- Area under the concentration time curve from time zero to the 6-hour post end of infusion timepoint (AUC₀₋₆) (Days 1, 8, and 29)
- Area under the concentration time curve over a dosing interval (AUC_τ) (Days 1 and 29)
- Area under the concentration-time curve from zero time to the last measurable time point (AUC_{0-*last*}) (Day 29)
- Maximum observed plasma concentration (C_{max}) (Days 1, 8, and 29)
- Time at which maximum plasma concentration occurs (t_{max}) (Days 1, 8, and 29)
- Concentration at the end of a dosing interval (C_{trough}) (Days 8, 15, 22, 29, and 36)
- Terminal elimination phase half-life (t_½) (Day 29 only)
- Total clearance (CL), calculated as dose/AUC_τ. (Day 29 only)
- Volume of distribution (V_d), calculated as dose/kel × AUC_τ, where kel is the apparent elimination rate-constant, computed by log linear regression of the terminal log linear segment of the plasma concentration versus time curve (Day 29 only).

[figure not shown]
The extent of CSF distribution as estimated by TB006 CSF concentrations on Day 36 will also be determined.

For Part 2 of the study, the PK analysis will be performed as secondary endpoint and will include:

- Maximum observed plasma concentration (C_{max}) (Days 1, 8, and 29)
- Concentration at the end of a dosing interval (C_{trough}) (Days 29 and 36)
- Area under the concentration-time curve from zero time to the last measurable time point (AUC_{0-*last*}) (Day 29)
- Terminal elimination phase half-life (t_½) (Day 29 only)

Note that no CSF will be collected in Part 2 of the study.

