3 OBJECTIVES AND ENDPOINTS

Table 3. Objectives and Endpoints

O	BJECTIVES - PART 1	ENDPOINTS
Pr	imary	
•	To determine the safety and tolerability of multiple doses of TB006	Safety endpoints, including the incidence of AEs and SAEs, clinical laboratory parameters, vital signs, ECGs, C-SSRS, and physical and neurological examinations, until Day 104 after the first TB006 dosing
•	To determine the PK profile of multiple doses of TB006	 PK parameters derived by noncompartmental analysis using the TB006 plasma concentration-time data, including, but not limited to and as appropriate: AUCtau: area under the concentration-time curve over a dosing interval Cmax: maximum observed plasma concentration tmax: time at which maximum plasma concentration occurs Ctrough: concentration at the end of a dosing interval t½: terminal elimination phase half-life CL: total clearance Vd: volume of distribution Extent of CSF distribution as estimated by TB006 CSF concentrations
•	To determine the maximum tolerated dose of multiple doses of TB006	Safety endpoints as above
•	To assess the immunogenicity of TB006 (production of anti-TB006 antibody)	Detection of anti-TB006 antibodies
•		Change from baseline through end of study on the Clinical Dementia Rating scale – Sum of Boxes total score

Protocol TB006AD2102

Protocol Date and Version: 15 Oct 2021; v 3.0

	 Change from baseline through end of study on the Cognitive Drug Research system battery score, composite scores and individual task measures Change from baseline through end of study on the MMSE score Change from baseline through end of study on the NPI score
--	---

OBJECTIVES - PART 2	ENDPOINTS
Primary	
To determine the clinical efficacy of TB006 in patients with mild to severe AD	Change from baseline through Day 104 on the Clinical Dementia Rating scale – Sum of Boxes total score
Secondary	
To determine the clinical efficacy of TB006 in patients with mild to severe AD	 Change from baseline through Day 36 on the Clinical Dementia Rating scale – Sum of Boxes total score Proportion of responders on the Clinical Dementia Rating scale – Sum of Boxes at Days 36 and 104 Change from baseline to Days 36 and 104 on the Cognitive Drug Research System Battery, composite scores and individual task measures Change from baseline to Days 36 and 104 on the MMSE score Change from baseline to Days 36 and 104 on the NPI score

Protocol TB006AD2102

Protocol Date and Version: 15 Oct 2021; v 3.0

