4.3 Justification for Dose

The selection of doses in the SAD study was made after a careful assessment of the preclinical pharmacology and toxicology data while allowing for cautious escalation to the highest safe exposures or the maximum tolerated dose (FDA, 2005). The doses planned for this study are tentative and may be adjusted based on safety, tolerability, and available PK data from the SAD study and the previous group(s) in this study. The intent is to maintain the safety margins as described here.

The preclinical safety of TB006 was explored in a definitive 1 month GLP toxicology study in cynomolgus monkeys. Doses used in this study were 10, 30, 100, and 200 mg/kg, administered qw for 5 doses. Mild lymphoid hyperplasia occurred in males at the 10, 100, and 200 mg/kg dose levels, but based on mild severity, lack of dose dependency and historical test facility data from

Protocol TB006AD2102

Protocol Date and Version: 15 Oct 2021; v 3.0

similar studies in cynomolgus monkeys, this finding was considered a species specific mild, reactive immune response and not an adverse toxicologic finding. No other adverse effects occurred, and so the NOAEL in cynomolgus monkeys dosed once qw for 4 weeks was 200 mg/kg. The mean Day 29 exposures associated with this dose were C_{max} and $AUC_{0-\tau}$ of $\sim 13,000 \ \mu g/mL$ and $\sim 135,000 \ h^*\mu g/mL$, respectively.

Using a body surface area calculation and a $10 \times$ safety factor, the maximum recommended safe starting dose would be 6.4 mg/kg, ~440 mg in a 70 kg person in the SAD study. Consideration, however, was given to preclinical efficacy data, where activity was demonstrated at a dose level of 10 mg/kg in mice. The HED conversion of this dose was approximately 70 mg in a 70 kg person. Subsequent planned doses in the SAD study were 200, 700, 2,100 and 5,000 mg. At the highest dose, a predicted safety margin from the NOAEL was estimated to be 8-fold on C_{max} and a 6-fold margin on $AUC_{0-\tau}$ based on early PK projections. Planned doses are to be modified based on safety and tolerability and PK (to retain these margins).

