If TB006 behaves like other IgG4 antibodies, the half-life will likely be longer than the approximate 10 to12 days observed in monkeys. Qw dosing will result in accumulation. Despite this, the safety and tolerability of a single dose is a conservative approach to estimating the safety and tolerability of the same dose divided into qw administration for 1 month. In addition, a similar conservative approach can be applied to establishing initial safety margin estimates by using one compartment simulations derived from monkey toxicokinetic data. The highest proposed dose of 1,000 mg qw (total regimen = 5,000 mg) affords a safety margin of > 8-fold on the C_{max} and 6-fold on the AUC from the NOAEL in the 1 month toxicology study. The lowest dose of 140 mg qw (total regimen = 700 mg) results in a safety margin of nearly 60- and 30-fold on the C_{max} and AUC, respectively. Using the HED conversion from the 200 mg/kg dose level in monkeys, the margins from the NOAEL range from ~30-fold at the lowest dose to ~5-fold at the highest dose for a 70 kg person.

The mid dose of 420 mg qw enables a cautious escalation between doses. Evidence of intolerance or other safety signals, or PK differences that result in reductions in safety margins from the SAD study or previous doses in this study, may necessitate a change in planned doses. While TB006 is a first in class anti-Gal-3 antibody, a wider array of approved IgG4 human monoclonal antibodies have been used clinically. Most of these target the immune system, and there appears to be a spectrum of negative effects, largely immune-mediated, when the total antibody dose gets too high. These and all other toxicities will be closely monitored. Dose escalation will either be modified or will cease when evidence of toxicity appears.

The proposed dose range covers a potentially efficacious dose to a projected supratherapeutic dose. Successful safety, tolerability and PK characterization of a wide dose range will enable efficient drug development. Traditionally, MAD studies employ the planned clinical dosing interval, and patients are dosed to steady state to determine steady state PK and safety. The projected half-life of TB006 is expected to enable monthly dosing in later clinical studies. The qw dosing schedule used in this study will enable a determination of multiple dose PK and provide an estimate of repeat dose safety and tolerability.

Protocol TB006AD2102

Protocol Date and Version: 15 Oct 2021; v 3.0

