9.4.2.2 Pharmacokinetics

Plasma and available CSF TB006 concentrations over time will be presented, showing both individual and mean concentrations. Plasma PK parameters will also be calculated and presented descriptively. Plasma PK parameters of interest may include C_{max} , t_{max} , C_{trough} , AUC_{tau} , CL, and Vd.

Additional PK analysis using a population PK approach may be used but will be reported separately from the clinical study report.

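### Part 1 clearance and volume are computed from the Day 29 dose/AUCtau as if at steady state, and SAP 6.4 lists PK values on days with no scheduled sample

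*SAP*

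**What the plan says.** Protocol Section 3 (Table 3) makes PK a Part 1 primary objective, with "PK parameters derived by noncompartmental analysis using the TB006 plasma concentration-time data"; the list includes "CL: total clearance Vd: volume of distribution". SAP 6.4 gives the formulas: "Total clearance (CL), calculated as dose/AUC_τ. (Day 29 only") for CL and, for Vd, "calculated as dose/kel × AUC_τ", also on Day 29 only.

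Protocol 4.3 describes the expected kinetics: "If TB006 behaves like other IgG4 antibodies, the half-life will likely be longer than the approximate 10 to12 days observed in monkeys", and "Qw dosing will result in accumulation". It presents dosing to steady state as the traditional approach in multiple-dose studies and claims only multiple-dose PK for this one.

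Neither SAP 6.4 nor the visible text of SAP 10.5 contains a steady-state check, a condition for reporting CL and Vd, a label, or an AUC integration rule. Protocol 9.4.2.2 leaves the alternative optional: "Additional PK analysis using a population PK approach may be used but will be reported separately from the clinical study report".

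SAP 6.4 lists Part 1 Ctrough on Days 8, 15, 22, 29 and 36, and Part 2 Cmax on Days 1, 8 and 29. The PK rows of the schedules (Protocol 1.3, Tables 1 and 2; SAP Appendix I, Tables 5 and 6) have no sample on Days 15 and 22 in Part 1 or on Day 8 in Part 2.

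**The concern.** Under linear kinetics, dose = CL × AUCtau holds only when the amount eliminated in a dosing interval equals the dose given. While drug is still accumulating, AUCtau is below its steady-state value and dose/AUCtau exceeds clearance. Vd inherits the error because it uses the same AUCtau. Followed as written, the study report would print these numbers as total clearance and volume with no qualification, and later readers would take them at face value.

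A second weakness sits beside the first. No PK sample is scheduled between 6 hours after the Day 29 infusion and Day 36, so most of the AUCtau is interpolated across one long gap by a rule the SAP does not name.

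The listed days are a separate matter. As the schedules stand, the Part 1 troughs on Days 15 and 22 and the Part 2 Cmax on Day 8 have no data behind them.

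**Working it through.** **1. Sample counts.** Protocol Tables 6 and 7 give 22 (Part 1) and 8 (Part 2) PK/ADA time points. From the schedules:
- Part 1: 3 days × 6 samples + D36, D64, D104 and E/D = 18 + 4 = 22.
- Part 2: 2 days × 2 samples + D36, D64, D104 and E/D = 4 + 4 = 8.

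Both reproduce without the disputed days. Adding Days 15 and 22 would give 24 in Part 1, or 23 without E/D, so neither matches. The Part 2 count is not decisive: without E/D it is 7, and one Day 8 sample would also make 8. There the schedule row is the evidence.

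**2. Fraction of steady state.** Inputs: five doses, tau = 7 d, so the Day 29 interval ends 35 d after the first dose; half-life t of 10 to 12 d from Protocol 4.3; 14 and 21 d are my assumptions for a longer human half-life. For one compartment:

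Day 29 AUCtau / steady-state AUCtau = 1 − exp(−ln2 × 35/t), and the error in CL = (1/fraction) − 1.

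| t (d) | Fraction | Error in CL |
|---|---|---|
| 10 | 0.912 | +9.7% |
| 12 | 0.868 | +15.3% |
| 14 (assumed) | 0.823 | +21.5% |
| 21 (assumed) | 0.685 | +46.0% |

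Vd carries the same percentage error if kel is correct.

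**3. Would the troughs reveal it?** With k = ln2/t per day, Day 29 pre-dose / Day 36 = (1 − e^(−28k))/(1 − e^(−35k)) = 0.939 at 10 d and 0.924 at 12 d. The Day 29 trough is only 6.1% to 7.6% below Day 36, which would look like a plateau.

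**4. Does one compartment fit?** Protocol 4.3 introduces monkey figures with "The mean Day 29 exposures associated with this dose were" a Cmax of about 13,000 µg/mL and an AUC of about 135,000 h·µg/mL. Their ratio is 135,000/13,000 = 10.4 h. One compartment predicts AUCtau/Cmax = (1 − e^(−168k))/k, with k per hour: 133 h at 10 d and 138 h at 12 d. Either those figures contain an error or the model does not fit, so the table in step 2 is only an illustration.

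**5. Two-phase check.** Noise-free; five 1-hour infusions 168 h apart; Day 29 samples pre-dose, at end of infusion, at +1, +2, +4 and +6 h, then Day 36. Assumed: fast half-life 1 or 2 d, terminal half-life 10 or 12 d, terminal share of AUC 0.5 or 0.8 (eight cases).

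| AUCtau used | Range of error in CL | Cases below zero |
|---|---|---|
| Exact (formula error alone) | +4.6% to +11.9% | 0 of 8 |
| Scheduled samples, log rule | −17.2% to +7.0% | 5 of 8 |
| Scheduled samples, linear rule | −34.6% to +2.4% | 7 of 8 |

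For one compartment on the same samples, the log rule gives +9.7% and +15.3% (10 and 12 d) and the linear rule +7.9% and +13.9%.

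The formula error is upward in every case. Interpolating across the gap after 6 h can outweigh it, so the AUC rule matters about as much as the steady-state issue.

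**The case against.** The strongest reply is that little hangs on these values. They are descriptive, from about six active patients per dose. Dose proportionality in SAP 10.5 uses AUCs and Cmax, and no test or decision rule uses CL or Vd. That stands, and it caps the weight of the point.

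The size and direction are also unsettled. The overstatement of 9.7% to 15.3% holds only under a model that the monkey figures call into question, and most of the two-phase cases give a net understatement. In the worst of them the steady-state part is only +4.6%; the rest is interpolation, which a non-steady-state label does not describe and the log rule does not remove. This stands as well, so the label should not be read as a correction for a known bias. It remains accurate whatever the net sign.

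The protocol's wording is flexible: Table 3 qualifies its list as appropriate, and 9.4.2.2 says which parameters may be included. That permits a qualification but does not supply one, and SAP 6.4 gives an explicit formula under the name of total clearance. Optional population PK, reported elsewhere, leaves the study report's values as they are.

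On the listed days, Protocol 8.5 allows samples to be added. Neither list nor schedule is therefore shown to be the wrong one; they simply disagree.

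**Conclusion.** The point holds. As written, SAP 6.4 gives the name of total clearance to a quantity that equals it only at steady state, which the plan does not check and, on the protocol's own account of the half-life, cannot assume. Under one compartment at 10 to 12 d, CL and Vd are overstated by 9.7% to 15.3%, and by more if the human half-life is longer. That figure assumes linear kinetics, exact weekly dosing and a model that may not fit. Under the assumed two-phase cases the net error in CL runs from −34.6% to +7.0% across the two AUC rules. The defect in the definition is certain; the size and sign of the error are not.

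The mismatch of days is confirmed by reading the schedules. Overall this is a minor-to-moderate point that should be corrected. It bears on how the Part 1 PK results are read and leaves escalation, safety and efficacy conclusions largely untouched.

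**What to change.** 1. In SAP 6.4, report Day 29 dose/AUCtau and dose/(kel × AUCtau) as apparent, non-steady-state values, not as total clearance and volume. State the AUC rule, for example linear-up/log-down. Add the missing brackets in the Vd formula, which is a clerical slip.
2. Only if true CL and Vd are wanted, take them from the population PK analysis that Protocol 9.4.2.2 already permits, with the compartment structure chosen by a criterion stated in advance.
3. Reconcile SAP 6.4 with the sampling schedules: remove Part 1 Ctrough on Days 15 and 22 and Part 2 Cmax on Day 8, unless samples on those days are formally added.

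Items 1 and 3 are SAP wording, with no new samples and no change to the protocol's noncompartmental definition. Because the relabelled parameters are named in the protocol's primary list, an entry in SAP Section 8 would be sensible. The price is that the study report carries no unqualified total clearance or volume. Item 2 needs modelling work and would be reported separately.
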